### 10.2. Populations for Analyses

#### 10.2.1. Study Participant Disposition

A detailed description of subject disposition will be provided at the end of the study.

#### 10.2.2. Study Participant Characteristics

The subject's age, sex, weight, BMI, height, race/subrace, and other demographic data will be summarized by dosing regimen and overall.

### 10.3. Statistical Analyses

Statistical analysis of this study will be the responsibility of Eli Lilly and Company or its designee.

Pharmacokinetic analyses will be conducted on the full analysis set. This set includes all data from all randomized subjects receiving the dose of LY3074828 with evaluable PK data in Part A. Safety analyses will be conducted for all subjects receiving a dose of LY3074828, whether or not they completed all protocol requirements.

Additional exploratory analyses of the data will be conducted as deemed appropriate. Study results may be pooled with the results of other studies for population PK analysis purposes to avoid issues with post-hoc analyses and incomplete disclosures of analyses.

No adjustments for multiple comparisons will be made.

### **10.3.1. Safety Analyses**

#### **10.3.1.1. Clinical Evaluation of Safety**

All IP and protocol procedure AEs and PCs will be listed, and if the frequency of events allows, safety data will be summarized using descriptive methodology.

The incidence of symptoms for each treatment will be presented by severity and by association with IP as perceived by the investigator. Symptoms reported to occur prior to study entry will be distinguished from those reported as new or increased in severity during the study. Each symptom will be classified by the most suitable term from the medical regulatory dictionary.

The number of IP- and device-related SAEs and any related PCs will be reported.

#### **10.3.1.2. Statistical Evaluation of Safety**

##### **10.3.1.2.1. *Injection-site Pain***

For Parts A and B, the intensity of pain at each injection site immediately (approximately within 5 minutes) following the start of the injection will be evaluated, as reported by the subject and measured according to the 0 to 100 mm VAS that forms part of the SF-MPQ. Assessments will also be performed at 15, 30, 60, 120, and 240 minutes post injection; however, the primary endpoint will be the 0-hour assessment.

Descriptive statistics will be used to summarize the intensity and type of pain at each time point as captured by the SF-MPQ.

In Part A, a linear fixed-effects model will be used to analyze the 0-hour (post-injection) pain VAS score and SF-MPQ total score. The model will include treatment (Reference or Test 1) as a fixed effect. The least squares (LS) means and differences in LS means (between Test 1 and Reference) will be presented along with the corresponding 90% CI. The distribution of the data will be explored prior to analysis to determine whether data transformation is required. It is possible that the pain scores will be 0 so if the distribution of the data implies that a log-transformation is required then the score may be updated to  $\log(VAS+1)$  to allow for the inclusion of the 0 values in the analysis.

A similar model will be used to analyze the 0-hour (post-injection) pain VAS score and SF-MPQ total score in Part B.

The following comparisons will be performed in Part B:

- Test 2 versus Test 3 (slow versus fast injection for 2-mL AI)
- Test 4 versus Test 5 (slow versus fast injection for 1-mL AI)

##### **10.3.1.2.2. *Duration of Injection***

The duration of the injection (measured in seconds) will be summarized for each drug delivery device for each dosing regimen.

#### **10.3.1.2.3. *Injection-site Assessments***

Incidence of erythema, induration, categorical pain, pruritus, edema, and bleeding will be listed and summarized by dosing regimen.

#### **10.3.1.2.4. *Statistical Evaluation of Other Safety Parameters***

Other safety parameters that will be assessed include clinical laboratory parameters, vital signs, and ECG parameters. The parameters, and changes from baseline (predose) where appropriate, will be listed and summarized using standard descriptive statistics. Additional analyses will be performed if warranted upon review of the data.

### **10.3.2. *Pharmacokinetic Analyses***

#### **10.3.2.1. *Pharmacokinetic Parameter Estimation***

For Part A, PK parameter estimates for LY3074828 will be calculated by standard noncompartmental methods of analysis.

The primary parameters for analysis will be AUC(0-∞), AUC(0-tlast), and Cmax for LY3074828. The secondary parameter for analysis will be the time to maximum observed drug concentration (tmax) of LY3074828. Other noncompartmental parameters, such as t1/2, apparent total body clearance of drug calculated after extra-vascular administration (CL/F), and apparent volume of distribution during the terminal phase after extra-vascular administration (Vz/F), may be reported.

For Part B, no PK parameters will be evaluated. Pharmacokinetic samples are collected only in conjunction with immunogenicity samples to provide serum concentrations of LY3074828 to aid in the interpretation of ADA data if needed. Samples will be stored and will only be sent for bioanalysis at a later date based on immunogenicity or safety results from Part B of the study.

#### **10.3.2.2. *Pharmacokinetic Statistical Inference***

For Part A, the AUC(0-∞), AUC(0-tlast), and Cmax will be log-transformed and analyzed using linear fixed-effects model. The model will include dosing regimen arm as a fixed effect. The dosing regimen differences between the Test 1 arm and the Reference arm will be back-transformed to present the ratios of geometric LS means and the corresponding 90% CI.

The tmax of LY3074828 between the 2 x 1-mL PFS (Reference) and the 1 x 2-mL PFS (Test 1) will be analyzed using a Wilcoxon rank sum test for Part A. Estimates of the median difference, 90% CIs, and p-values from the Wilcoxon rank sum test will be calculated.

Additional PK analyses may be conducted for Part A if deemed appropriate.

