## **2. Schedule of Activities**

## Study Schedule Protocol I6T-MC-AMAQ – Part A

Procedure	Screening	Days														Comments
		≤28 days	-1	1	2	4 ±1d	8 ±1d	11 ±1d	15 ±2d	22 ±2d	29 ±2d	43 ±2d	57 ±3d	71 ±3d	85/ED ±3d	
Informed consent	X															
Review / confirm inclusion/exclusion criteria	X	X														Any time prior to dosing.
Subject admission to CRU		X														
Subject discharge from CRU				X												
Outpatient visit	X				X	X	X	X	X	X	X	X	X	X		
Randomization			X													Subjects randomized to 1 x 2-mL or 2 x 1-mL PFS arm.
LY3074828 injection			X													Doses administered by investigative site staff.
Stopwatch recording			X													Stopwatch is the source for injection duration capture.
Medical history	X															
Weight, height, and BMI	X															
Vital signs: blood pressure, pulse rate, temperature (hour)	X	X	0, 6	24	X	X	X	X	X	X	X			X		Times with respect to start of dosing. Single ECGs to be collected. Zero-hour collection within 30 minutes before dosing. Time allowance for 6- and 24-hour time points: ±30 and ±90 minutes, respectively. For vital sign assessments, temperature need only be included at predose and when clinically indicated.
12-lead ECG (hour)	X		0	24										X		
Physical examination / medical assessment	X	X		X									X	X		Full physical examination/medical assessment at screening. Symptom-directed physical examination/medical assessment at all other time points, and as deemed necessary by the investigator.
AE review	X	X	X	X	X	X	X	X	X	X	X	X	X	X		AE only after signing ICF. Product complaints and device-related AEs collected as appropriate.
QuantiFERON®-TB Gold test	X															

Procedure	Screening	Days														Comments
		≤28 days	-1	1	2	4 ±1d	8 ±1d	11 ±1d	15 ±2d	22 ±2d	29 ±2d	43 ±2d	57 ±3d	71 ±3d	85/ED ±3d	
Serology	X															See Appendix 2 for test details.
Ethanol test and urine drug screen	X	X														May be repeated at the discretion of the investigator. Ethanol test may be either breath or urine testing. See Appendix 2 for test details.

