#### 3.2. Background

LY3074828 is a humanized immunoglobulin G4-variant monoclonal antibody that is directed against the p19 subunit of interleukin-23 (IL-23) and does not bind interleukin-12. LY3074828 is being developed for the treatment of autoimmune diseases in which the IL-23 pathway is thought to have a significant pathogenic role. Neutralization of IL-23 with an anti-mouse IL-23 surrogate antibody (directed against the p19 subunit) significantly reduced the development of arthritis and inhibited ileal inflammation in a mouse model of spondyloarthropathy with bowel inflammation (Ruutu et al. 2012). Additionally, neutralization of IL-23 significantly reduced the disease score in the relapsing-remitting experimental autoimmune encephalomyelitis (multiple sclerosis-like) model in mice. Anti-IL-23 antibody also demonstrated some efficacy in preclinical arthritis models, depending on the timing of intervention (Cornelissen et al. 2013).

LY3074828 has been evaluated in 5 healthy subjects (single 120-mg SC doses) and in 33 subjects with plaque psoriasis (single ascending intravenous [IV] doses of 5, 20, 60, 120, 200, 350, or 600 mg) in Study I6T-MC-AMAA (AMAA). Furthermore, 43 healthy Japanese and Caucasian subjects were administered single IV doses of 60, 200, 600, or 1200 mg LY3074828, or placebo, or single SC doses of 200 mg LY3074828, or placebo, in Study I6T-MC-AMAD (AMAD).

No serious adverse events (SAEs) were reported in either study. There were no drug-related treatment-emergent adverse events (TEAEs) of National Cancer Institute Common Terminology Criteria for Adverse Events Grade 2 or higher reported in Study AMAA, and no infusion reactions, injection-site reactions, or adverse events (AEs) considered related to study drug were reported in Study AMAD. There were no dose-dependent trends in AEs, or clinically important changes in vital signs, electrocardiograms (ECGs), or clinical laboratory results across both studies that were considered to be related to the study drug. Pharmacokinetic results obtained

from Study AMAA indicated that serum exposure of LY3074828 increases in a dose-proportional manner, and that the mean half-life associated with the terminal rate constant ( $t_{1/2}$ ) was 10.5 days, which did not appear to be dependent on dose. Maximum concentrations were observed 3 days postdose following SC administration and, based on the area under the concentration versus time curve (AUC), the SC bioavailability was 40%.

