## 10. Statistical Considerations and Data Analysis

### 10.1. Sample Size Determination

A total of approximately 72 subjects (approximately 36 subjects per study Parts A and B) who fulfill the eligibility criteria will be randomized to 1 of 2 dosing regimen arms within their assigned study part, with 18 subjects randomized to each arm in order to ensure completion of 16 subjects in each. The estimated total variability (coefficient of variation) in AUC from time zero to infinity  $AUC(0-\infty)$ , AUC from time zero to time  $t$ , where  $t$  is the last sample with a measurable concentration ( $AUC[0-t_{last}]$ ), and maximum observed drug concentration ( $C_{max}$ ) was 49%, 49%, and 23%, respectively, in Study AMAA following a single SC dose of 120 mg LY3074828. The coefficient of variation of 49% was used for precision estimates and is assumed for all dosing regimen arms. A sample size of 64 subjects will provide a precision, in log scale, of approximately 0.28 for the geometric means ratio in  $AUC(0-\infty)$ ,  $AUC(0-t_{last})$ , and  $C_{max}$  of 1- to 2-mL solution formulation injection. That is, there is a 90% probability that the half-length of the 90% confidence interval (CI) of the geometric means ratio in log scale is not larger than 0.28. Subjects who are randomized but not administered treatment, or subjects that are administered treatment but do not have PK and ADA samples collected up to and including Day 57, may be replaced (maximum of 4 per arm per study part) to ensure that approximately 16 subjects from each dosing regimen arm complete the study.

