### **9.2 Demographics and Subject Disposition**

Subject disposition will be listed. The demographic variables age, sex, race, ethnicity, body weight, height and body mass index will be summarized and listed. All other demographic variables will be listed only.

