#### **9.3.2 Pharmacokinetic Statistical Methodology**

For Part A, the  $AUC(0-\infty)$ ,  $AUC(0-t_{last})$ , and  $C_{max}$  will be log-transformed and analyzed using a linear fixed-effects model. The model will include dosing regimen arm as a fixed effect. The dosing regimen differences between the Test 1 arm and the Reference arm will be back-transformed to present the ratios of geometric least squares means and the corresponding 90% CI.

Example SAS code:

```
proc mixed data=xxx;
  by parameter;
  class arm;
  model log_pk = arm / residual;
  lsmeans arm / alpha=0.1 cl pdiff;
  ods output lsmeans=lsmeans;
  ods output diff=diffs;
```

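### Part A's primary PK model has dosing arm as its only term; prespecifying log screening body weight as a covariate would be a cheap gain in precision if weight predicts exposure

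*Protocol*

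**What the plan says.** Protocol 10.3.2.1 makes AUC(0-∞), AUC(0-tlast) and Cmax the primary PK parameters. Protocol 10.3.2.2 log-transforms them, fits a linear model and states "The model will include dosing regimen arm as a fixed effect". The difference between Test 1 and Reference is "back-transformed to present the ratios of geometric LS means and the corresponding 90% CI". SAP 9.3.2 repeats this, and its example SAS code reads "model log_pk = arm / residual".

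The Part A Schedule of Activities lists "Weight, height, and BMI" at screening. The only planned use of weight is descriptive: Protocol 10.2.2 summarizes it by regimen, and SAP 9.2 says "body weight, height and body mass index will be summarized and listed". Protocol 7.2 describes a computer-generated randomization schedule and names no stratification factor. Table AMAQ.2 gives 250 mg to both arms. Inclusion criteria 1 and 3 admit both sexes with BMI 18.0 to 32.0 kg/m² and set no weight limits.

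On variability, Protocol 10.1 says "The coefficient of variation of 49% was used for precision estimates and is assumed for all dosing regimen arms". The CV for Cmax is given as 23%.

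**The concern.** With a fixed dose and no weight limits, dose per kilogram differs between subjects. Part A is a parallel comparison, which Protocol 5.4 justifies by the long half-life, so there is no within-subject control. All between-subject variation in exposure, including any part that weight could explain, stays in the residual. Neither the randomization nor the model deals with body size.

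The comparison of the 2 x 1-mL and 1 x 2-mL syringes on exposure rests on three ratios and their 90% intervals, from about 16 subjects per arm. If weight is related to exposure, leaving it out costs precision and lets a chance difference in mean weight between the arms move the observed ratio. The sentence that allows additional PK analyses does not fill the gap, because it is optional and unspecified. In an open-label study whose data may be analyzed while it is running (Protocol 10.3.6 and 10.3.7), a weight adjustment added after an imbalance has been seen would look chosen for its result.

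**Working it through.** **Inputs from the documents.** CV 49% for both AUCs and 23% for Cmax (Protocol 10.1); 16 completers per arm (Protocol 5.2 and 10.1); 90% interval on the log scale; one model term, arm.

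**Assumed input.** R-squared (R²) is the within-arm share of log-parameter variance explained by log weight. The documents give no such figure, so a range from 0 to 40% is shown.

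**Step 1: the plan's own figure.** The log-scale SD is s = √ln(1 + CV²). For AUC, √ln(1 + 0.49²) = 0.4639. For Cmax, √ln(1 + 0.23²) = 0.2270.

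Unadjusted half-length = t(0.95, 30) × s × √(2/16).
- AUC: 1.697 × 0.4639 × 0.3536 = 0.278, or ratio limits of about 0.757 to 1.321 around 1. This matches the plan's approximately 0.28, read as an expected half-length for 16 versus 16.
- Cmax: 1.697 × 0.2270 × 0.3536 = 0.136.

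**Step 2: add log weight.** The residual SD becomes s√(1 − R²) and the residual degrees of freedom fall from 30 to 29. Estimating the slope also adds an average variance penalty for chance imbalance in the covariate, 1 + 1/28:

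adjusted half-length = t(0.95, 29) × s × √(1 − R²) × √(2/16) × √(1 + 1/28).

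For AUC at R² = 0 this is 1.699 × 0.4639 × 0.3536 × 1.0177 = 0.284.

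**Step 3: chance imbalance.** If mean log weight differs between arms by one standard error, the unadjusted log ratio moves by √R² × s × √(2/16). That is √R² × 0.164 for AUC and √R² × 0.080 for Cmax.

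| Assumed R² | AUC half-length | Change from 0.278 | AUC limits around 1 | AUC ratio shift, one SE | Cmax ratio shift, one SE |
|---|---|---|---|---|---|
| 0 | 0.284 | 1.9% wider | 0.753 to 1.328 | none | none |
| 5% | 0.276 | 0.7% narrower | 0.758 to 1.318 | 3.7% | 1.8% |
| 10% | 0.269 | 3.4% narrower | 0.764 to 1.309 | 5% | 2.6% |
| 20% | 0.254 | 8.9% narrower | 0.776 to 1.289 | 8% | 3.7% |
| 30% | 0.237 | 14.8% narrower | 0.789 to 1.268 | 9% | 4.5% |
| 40% | 0.220 | 21.1% narrower | 0.803 to 1.246 | 11% | 5.2% |

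At a given R² the proportional change for Cmax is the same: 0.136 × 0.911 = 0.124 at 20%, for example. R² need not be equal for AUC and Cmax.

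**Step 4: break-even.** The two half-lengths are equal when 1 − R² = [t(0.95, 30) / t(0.95, 29)]² / (1 + 1/28), which gives R² of about 3.7%. Below that, adjustment loses slightly.

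**Step 5: simulation check.** In 40,000 simulated trials per R² value, the ratio of mean adjusted to mean unadjusted half-length agreed with the formula (1.019, 0.967, 0.911 and 0.852 at R² = 0, 10%, 20% and 30%). The adjusted interval was the narrower one in 20%, 65%, 87% and 96% of trials respectively. Coverage of both intervals was between 89.8% and 90.3% throughout.

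**The case against.** The strongest reply is that nothing in the plan is wrong. Protocol and SAP agree. Under randomization the arm-only 90% interval keeps its nominal coverage, and its width already allows for chance imbalance. That stands in full. A reader might infer from the missing covariate that the planned ratio is biased or the interval invalid; the documents and the simulated coverage do not support that.

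The second reply is that the benefit cannot be established from these documents. Protocol 3.2 reports dose proportionality, half-life and bioavailability, but no relation between weight and exposure, and no SD of weight is given. So a reader may not take it as fact that the planned intervals are wider than necessary. This also stands: the gain is conditional. Below an R² of about 3.7% adjustment does slight harm, and at 10% the adjusted interval would still be the wider one in about a third of trials.

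Third, the plan sets no equivalence margin, so no stated decision changes if an interval narrows by 3% to 15%. That is correct and limits the weight of the point. It does not remove it, because the objective is to evaluate PK and the interval is how that evaluation is reported.

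Fourth, the plan already permits further PK analyses and pooled population PK. Both are optional and neither names weight, so this answers the point only in part.

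**Conclusion.** This is a cheap improvement, not an error. What is certain is the omission: arm is the only model term in both documents, weight is collected and then only described, and no weight stratification is described. What is conditional is the gain. The trade is uneven in favor of adjustment: at worst an interval about 2% wider on average, against one about 9% to 15% narrower at an assumed R² of 20% to 30%.

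The absolute half-lengths rest on the planning CVs and on 16 completers per arm. The CVs come from Study AMAA, of which Protocol 3.2 says "LY3074828 has been evaluated in 5 healthy subjects (single 120-mg SC doses"), so they are themselves uncertain. The percentage changes in half-length do not depend on the CV.

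One further inference should be resisted. Protocol 10.1 and SAP 7 attach a 90% probability to the half-length of 0.28. At 16 per arm and CV 49% without a covariate, that probability is about 55% and the 90%-assured half-length is about 0.322. A reader might see the covariate as the remedy, since an R² of about 28% would bring the assured value to 0.28. The documents supply no such R². The sample-size statement is a separate issue, which adding weight does not correct.

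**What to change.** In Protocol 10.3.2.2 and SAP 9.3.2, prespecify the primary model for each of the three parameters as log(PK parameter) = arm + log(screening body weight), and keep the arm-only model as a sensitivity analysis. In the SAS code this adds one continuous variable to the MODEL statement; the LSMEANS statement and the reported ratio of geometric LS means stay as they are. State the assumed range of R² beside the change.

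Settle this before any PK results by arm are reviewed. That includes the Part A data review at about Day 57 (Protocol 10.3.6) and the exploratory interim analysis (Protocol 10.3.7). If arm-level PK has already been seen, keep the arm-only model as primary and report the weight-adjusted model as a supporting analysis, with the timing of the decision stated.

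The cost is one sentence in each document, one covariate and one residual degree of freedom, with no new data. The downside is an expected interval about 2% wider if weight turns out to be unrelated to exposure.

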### **10.3.3. *Pharmacodynamic Analyses***

This section is not applicable for this study.

### **10.3.4. *Pharmacokinetic/Pharmacodynamic Analyses***

This section is not applicable for this study.

### ***10.3.5. Evaluation of Immunogenicity***

The frequency of formation of antibodies to LY3074828 will be determined.

Treatment-emergent ADAs are those that are induced or boosted by exposure to study drug, with a 4-fold or greater increase in titer compared to baseline if ADAs were detected at baseline, or a titer 2-fold greater than the minimum required dilution (1:10) if no ADAs were detected at baseline.

If a neutralization assay is performed, the frequency of neutralizing antibodies will be determined. The relationship between the presence (or absence) of antibodies and clinical parameters (AEs) will be assessed. Likewise, the relationship between the presence of antibodies and the PK parameters or concentrations of LY3074828 may be assessed if deemed appropriate.

### ***10.3.6. Data Review During the Study***

Data may be accessed and analyzed while the trial is ongoing, but no changes to the study design are planned. An assessment committee will not be formed.

For Parts A and B of the study, available safety data will be reviewed at approximately Day 30 in order to review emerging safety and tolerability data.

For Part A of the study, data review is scheduled to occur when safety and PK data through approximately Day 57 (8 weeks postdose) become available for at least 12 subjects from each dosing regimen arm. The purpose of the data review is to trigger Chemistry, Manufacturing, and Control processes with respect to LY3074828 formulation, and to inform dose selection for Phase 3 first registration.

### ***10.3.7. Interim Analyses***

An exploratory interim analysis is planned for this study. This will be for internal purposes only.

## **Appendix 1. Abbreviations and Definitions**

---

Term	Definition
ADA	anti-drug antibody
AE	adverse event: Any untoward medical occurrence in a patient or clinical investigation subject administered a pharmaceutical product that does not necessarily have a causal relationship with this treatment. An AE can therefore be any unfavorable and unintended sign (including an abnormal laboratory finding), symptom, or disease temporally associated with the use of a medicinal (investigational) product, whether or not related to the medicinal (investigational) product.
AI	autoinjector
ALP	alkaline phosphatase
ALT	alanine aminotransferase
AUC	area under the concentration versus time curve
AUC(0-∞)	area under the concentration versus time curve from time zero to infinity
AUC(0-tlast)	area under the concentration versus time curve from time zero to time t, where t is the last sample with a measurable concentration
BMI	body mass index
CD	Crohn's disease
CI	confidence interval
CL/F	apparent total body clearance of drug calculated after extra-vascular administration
Cmax	maximum observed drug concentration
complaint	A complaint is any written, electronic, or oral communication that alleges deficiencies related to the identity, quality, purity, durability, reliability, safety or effectiveness, or performance of a drug or drug delivery system.
compliance	Adherence to all the trial-related requirements, good clinical practice requirements, and the applicable regulatory requirements.
confirmation	A process used to confirm that laboratory test results meet the quality requirements defined by the laboratory generating the data and that Lilly is confident that results are accurate. Confirmation will either occur immediately after initial testing or will require that samples be held to be retested at some defined time point, depending on the steps required to obtain confirmed results.
CP	clinical pharmacologist
CPK	creatine phosphokinase
CRP	clinical research physician
CRU	clinical research unit

ECG	electrocardiogram
eCRF	electronic case report form
ED	early discontinuation
enroll	The act of assigning a subject to a treatment. Subjects who are enrolled in the trial are those who have been assigned to a treatment.
enter	Subjects entered into a trial are those who sign the informed consent form directly or through their legally acceptable representatives.
GCP	good clinical practice
GMP	good manufacturing practice
GPS	Global Patient Safety
HIV	human immunodeficiency virus
IB	Investigator's Brochure
ICF	informed consent form
ICH	International Council for Harmonisation
IFU	Instructions for Use
IL-23	interleukin-23
informed consent	A process by which a subject voluntarily confirms his or her willingness to participate in a particular trial, after having been informed of all aspects of the trial that are relevant to the subject's decision to participate. Informed consent is documented by means of a written, signed, and dated informed consent form.
interim analysis	An interim analysis is an analysis of clinical trial data, separated into treatment groups, that is conducted before the final reporting database is created/locked.
investigator	A person responsible for the conduct of the clinical trial at a trial site. If a trial is conducted by a team of individuals at a trial site, the investigator is the responsible leader of the team and may be called the principal investigator.
IP	investigational product
IRB	institutional review board
IV	intravenous(ly)
LS	least squares
open-label	A study in which there are no restrictions on knowledge of treatment allocation, therefore the investigator and the study participant are aware of the drug therapy received during the study.

PC	product quality complaint
PFS	pre-filled syringe
PK	pharmacokinetic(s)
Q4W	every 4 weeks
Q8W	every 8 weeks
SAE	serious adverse event
SC	subcutaneous(ly)
screen	The act of determining if an individual meets minimum requirements to become part of a pool of potential candidates for participation in a clinical trial.
SF-MPQ	Short Form McGill Pain Questionnaire
SFS	semi-finished syringe
SUSAR	suspected unexpected serious adverse reaction
t1/2	half-life associated with the terminal rate constant
TB	tuberculosis
TBL	total bilirubin
TE-ADA	treatment-emergent anti-drug antibody
TEAE	treatment-emergent adverse event: Any untoward medical occurrence that emerges during a defined treatment period, having been absent pretreatment, or worsens relative to the pretreatment state, and does not necessarily have to have a causal relationship with this treatment.
tmax	time to maximum observed drug concentration
ULN	upper limit of normal
VAS	visual analog scale
Vz/F	apparent volume of distribution during the terminal phase after extra-vascular administration

---

